## 2.2. Study Design

This is a randomized withdrawal, double-blind, placebo-controlled study of subjects from 2 to <18 years of age with JIA.

All eligible subjects enrolled in the study will initially receive open-label tofacitinib for 18 weeks (run-in phase). At the end of the 18 week run-in phase, only subjects who achieve at least a JIA ACR 30 response will be randomized to the 26 week double-blind, placebo-controlled phase. Subjects who do not achieve a JIA ACR 30 response at this time point will be discontinued from the study. Subjects who experience a single episode of disease flare at any time during the study (including the open-label run-in and double-blind phase) will also be discontinued from the study.

CCI

Subjects who are eligible for the 26 week double-blind phase will be randomized (1:1 ratio) to either active tofacitinib or placebo. For subjects with polyarticular course JIA (ie, extended oligoarthritis, polyarthritis RF+, polyarthritis RF-, systemic JIA with active arthritis but without active systemic features), randomization will be stratified by JIA category and baseline CRP (normal CCI, above normal CCI). For subjects with psoriatic and enthesitis-related arthritis, randomization will be stratified by JIA category.

CCI

Approximately 210 subjects will be enrolled in the open-label run-in phase. Among subjects with polyarticular course JIA, stratification will target enrollment of at least 50% with a baseline CRP above the upper limit of normal.

The cohort of subjects with polyarticular course JIA will have at least 170 subjects enrolled in the run-in phase with the minimum number of JIA categories as follows: 24 with extended oligoarthritis, 20 with polyarthritis RF+, 62 with polyarthritis RF-, 20 with systemic JIA with active arthritis but without active systemic features. Additional cohorts (ie, psoriatic and enthesitis-related arthritis) will include a minimum of 20 subjects with psoriatic arthritis, and 20 subjects with enthesitis-related arthritis. The overall target minimum number of subjects to be enrolled in the study by age is as follows: 20 subjects 2 to <6 years, 20 subjects 6 to <12 years, and 20 subjects 12 to <18 years. The Sponsor will monitor enrollment and periodically notify investigator sites regarding the status of enrollment in the various JIA categories and age groups.

The duration of subject participation among those who complete the study (without discontinuation) is expected to be approximately 44 weeks. Pediatric blood tubes will be used (reduced volume) for testing to determine eligibility, monitor safety, and measure PK.

The study will be conducted over a period of approximately 3 years. CCI

CCI

CCI

CCI

CCI

### **3. ENDPOINTS AND BASELINE VARIABLES: DEFINITIONS AND CONVENTIONS**

#### **3.1. Primary Endpoint**

The primary endpoint of this study is:

- Occurrence of disease flare (according to PRCSG/PRINTO Disease Flare criteria) by Week 44/End of Study (Week 26 of the double-blind phase).

Only disease flare during the double-blind phase will be counted as primary endpoint.

Disease flare (except assigning as flare after discontinuation) will be derived by the Centralized Coordinating Center (CCC) using Erythrocyte Sedimentation Rate (ESR) in real-time, and double-blind baseline will be used to determine disease flare. CCI

[Redacted]

### 3.2. Secondary Endpoints

#### 3.2.1. Key Secondary Endpoints

- Achieving JIA ACR 30-50-70 response at Week 44/End of Study (Week 26 of the double-blind phase); open-label run-in baseline will be used to determine ACR response.

CCI [Redacted]

- Change from double-blind baseline in CHAQ disability index at Week 44/End of Study (Week 26 of the double-blind phase).

- CCI [Redacted]

#### 3.2.2. Secondary Endpoints in the Double-Blind Phase

- Disease flare and JIA ACR inactive disease during double-blind phase will be derived by the CCC using ESR in real-time, and other secondary endpoints during the double-blind phase will be derived by Pfizer. CCI

All secondary endpoints with data collected in the double-blind phase (from randomization/Week 18 to Week 44/EOS) are:

- Occurrence of disease flare (according to PRCSG/PRINTO Disease Flare criteria) at each scheduled visit up to Week 44 (Week 26 of the double-blind phase) in the double-blind phase. CCI

CCI [REDACTED]

- Time to disease flare in the double-blind phase. Time to disease flare is measured in number of days since randomization (day of disease flare – day of randomization +1) into the double-blind phase. CCI [REDACTED]

[REDACTED]

- Achieving JIA ACR 30-50-70-90-100 response at each scheduled visit up to Week 44 (Week 26 of the double-blind phase) in the double-blind phase; open-label run-in baseline will be used to determine ACR response;
- Change from double-blind baseline in JADAS-27 CRP, JADAS-27 ESR, and achieving JADAS minimum disease activity and inactive disease at each scheduled visit up to Week 44 (Week 26 of the double-blind phase) in the double-blind phase;
- Achieving JIA ACR inactive disease at each scheduled visit up to Week 44 (Week 26 of the double-blind phase) in the double-blind phase, and achieving clinical remission at week 44 (double-blind week 26); CCI [REDACTED]

[REDACTED]

- Change from double-blind baseline in each JIA ACR core set variable at each scheduled visit up to Week 44 (Week 26 of the double-blind phase) in the double-blind phase;
- Change from open-label run-in baseline in each JIA ACR core set variable at each scheduled visit up to Week 44 (Week 26 of the double-blind phase) in the double-blind phase;
- Change from double-blind baseline in CHQ responses at each scheduled visit up to Week 44 (Week 26 of the double-blind phase) in the double-blind phase;
- Change from double-blind baseline in CHAQ responses at each scheduled visit up to Week 44 (Week 26 of the double-blind phase) in the double-blind phase.

- The ‘each scheduled visit’ means the visit in the visit window as defined in [Appendix 9.3](#) throughout the study.

### 3.2.3. Secondary Endpoints in the Open-Label Run-in Phase

- Disease flare and JIA ACR inactive disease during open-label run-in phase and DB phase, and ACR 30 response at week 18 CCI [REDACTED]
- The secondary efficacy endpoints with data collected in open-label run-in phase (from Day 1 to randomization/Week 18) are:
- Occurrence of disease flare at each scheduled visit in the open-label phase. CCI [REDACTED]
- Time to disease flare in the open-label run-in phase. Time to disease flare is measured in number of days since Day 1 (day of disease flare – Day 1 +1) into the open-label run-in phase. Day 1 is defined as the day of first dose of study drug in open-label run-in phase. CCI [REDACTED]
- Achieving JIA ACR 30-50-70-90-100 response at each scheduled visit in the open-label run-in phase; JIA ACR 30-50-70-90-100 response is determined based on the open-label run-in baseline.
- Change from open-label run-in baseline in JADAS-27 CRP, JADAS-27 ESR, and achieving JADAS minimum disease activity and inactive disease at each scheduled visit in the open-label run-in phase;
- Achieving JIA ACR inactive disease at each scheduled visit in the open-label run-in phase; percentage of subjects experiencing at least one JIA ACR inactive disease during open-label phase.
- Change from open-label run-in baseline in each JIA ACR core set variable at each scheduled visit in the open-label run-in phase.
- Change from open-label run-in baseline in CHQ responses at each scheduled visit in the open-label run-in phase.
- Change from open-label run-in baseline in CHAQ responses at each scheduled visit in the open-label run-in phase.

- Taste acceptability of tofacitinib oral solution (Like very much, Like a little, Not Sure, Dislike a little, Dislike very much), if applicable, on Day 14 of the open-label run-in phase.
- CCI [REDACTED]
- The same secondary endpoints in the open-label run-in phase will also be calculated for ERA and PsA subjects.

### 3.2.4. Secondary Endpoints Specific for ERA and PsA in Both Open-Label Run-In Phase and Double-Blind Phase

- Secondary endpoints in both open-label run-in phase and double-blind phase are all ERA and PsA specific endpoints. For details of the derivation of these endpoints, see [Appendix 9.2.9](#) to [9.2.10](#).

Open-label phase (Day 1 to randomization/Week 18):

- In subjects with ERA: Change from open-label run-in baseline in the Tender Enteseal Assessment, Modified Schober's Test, Overall Back Pain and Nocturnal Back Pain responses at each scheduled visit in the open-label run-in phase;
- In subjects with PsA: Change from open-label run-in baseline in the body surface area (BSA) affected with psoriasis and PGA of psoriasis assessments at each scheduled visit in the open-label run-in phase.

Double-blind phase (randomization/Week 18 to Week 44/EOS):

- In subjects with ERA: Change from double-blind baseline in the Tender Enteseal Assessment, Modified Schober's Test, Overall Back Pain and Nocturnal Back Pain responses at each scheduled visit up to Week 44 (Week 26 of the double-blind phase) in the double-blind phase;
- In subjects with PsA: Change from double-blind baseline in the body surface area (BSA) affected with psoriasis and PGA of psoriasis assessments at each scheduled visit up to Week 44 (Week 26 of the double-blind phase) in the double-blind phase.
- The 'each scheduled visit' means the visit in the visit window as defined in [Appendix 9.2.3](#) throughout the study.

## 3.3. Other Endpoints

### 3.3.1. PK Endpoints

- Plasma tofacitinib concentrations during the open-label run-in phase.

CCI [REDACTED]

CCI

### 3.5. Safety Endpoints

The safety endpoints of this study are:

- Occurrence of active uveitis (according to SUN criteria) at each scheduled visit in the open-label run-in and double-blind phase;
- Incidence and severity of adverse events, with focus on serious infections, cytopenias, malignancies, cardiovascular diseases and gastrointestinal perforations;
- Incidence of clinical laboratory abnormalities and change from baseline in clinical laboratory values;
- Incidence of abnormalities in physical examination and incidence of significant changes from baseline at final visit for physical examination;
- Incidence of vital sign abnormalities and change from baseline in vital sign measures;
- Validated assessments of growth and pubertal development (Tanner Stage of Development);

The ‘each scheduled visit’ means the visit in the visit window as defined in [Appendix 9.2.3](#) throughout the study.

## 4. ANALYSIS SETS

Data for all subjects will be assessed to determine if subjects meet the criteria for inclusion in each analysis population prior to unblinding and releasing the database and classifications will be documented per standard operating procedures. Table 2 listed all the analysis sets and their corresponding analyses in the study.

**Table 2. Summary of Different Analysis Sets**

Analysis set	Brief description	Efficacy analysis	Safety analysis
DBFAS	Subjects randomized to DB phase, received at least one dose of study medication in DB phase, reported under randomized treatment	None	None
DBJAS	pJIA subjects in DBFAS	Primary endpoint, key secondary endpoints and secondary endpoints in DB phase for pJIA	None
DBERA	ERA subjects in DBFAS	Secondary endpoints in DB phase for ERA, ERA specific endpoints in DB phase	None
DBPsA	PsA subjects in DBFAS	Secondary endpoints in DB phase for PsA, PsA specific endpoints in DB phase	None
DBJPP	Subjects with no major protocol violations in the DBJAS	Primary endpoint	None
DBSAS	Subjects received at least one dose of study medication in DB phase, reported under received treatment	None	All DB safety analyses
OLFAS	Subjects enrolled, received at least one dose of study medication in OL phase	Taste acceptability	All OL safety analyses
OLJAS	pJIA subjects in OLFAS	Secondary endpoints in OL phase for pJIA	None

Analysis set	Brief description	Efficacy analysis	Safety analysis
OLERA	ERA subjects in OLFAS	Secondary endpoints in OL phase for ERA, ERA specific endpoints in OL phase	None
OLPsA	PsA subjects in OLFAS	Secondary endpoints in OL phase for PsA, PsA specific endpoints in OL phase	None

#### **4.1. Double-Blind Full Analysis Set (DBFAS)**

The double-blind full analysis set (DBFAS) consists of all subjects randomized to the double-blind phase who received at least one dose of study medication in the double-blind phase. Subjects will be reported under the treatment they were randomized to. In this study, no efficacy analyses will be performed on the DBFAS, all efficacy analyses will be done on the following subsets of the DBFAS.

##### **4.1.1. Double-Blind Polyarticular Course JIA Analysis Set (DBJAS)**

The double-blind polyarticular course JIA analysis set (DBJAS) consists of all subjects included in the DBFAS with polyarticular course JIA. The double-blind polyarticular course JIA analysis set is the primary efficacy analysis set of the study.

##### **4.1.2. Double-Blind ERA Analysis Set (DBERA)**

The double-blind ERA analysis set (DBERA) consists of all subjects included in the DBFAS with ERA.

##### **4.1.3. Double-Blind PsA Analysis Set (DBPsA)**

The double-blind PsA analysis set (DBPsA) consists of all subjects included in the DBFAS with PsA.

#### **4.2. Double-Blind Polyarticular Course JIA Per Protocol Analysis Set (DBJPP)**

The double-blind polyarticular course JIA per-protocol analysis set (DBJPP) will consist of all subjects included in the double-blind polyarticular course JIA analysis set (see [Section 4.1.1](#)) who have no major protocol violations with regard to inclusion criteria, exclusion criteria, or study conduct.

Inclusion in the DBJPP analysis set will be determined prior to un-blinding of the study. Efficacy results for the DBJPP analysis set will be produced as part of a sensitivity analysis, supporting the analysis of the primary endpoint.

If there are few major protocol deviations impacting the primary analysis, the study team will decide whether to have a DBJPP analysis or not before un-blinding of the study.

See the definition of protocol deviations that relate to statistical analysis/populations in [Appendix 9.4](#).

### **4.3. Double-Blind Safety Analysis Set (DBSAS)**

The double-blind safety analysis set (DBSAS) consists of all subjects who have received at least one dose of study medication in double-blind phase. Subjects will be reported under the treatment which they received.

### **4.4. Other Analysis Sets**

#### **4.4.1. Open-Label Run-In Phase Full Analysis Set (OLFAS)**

The open-label run-in phase full analysis set (OLFAS) consists of all subjects who were enrolled into the open-label run-in phase of the study and received at least one dose of study medication in the open-label run-in phase. This will be the same as the open-label run-in safety analysis set.

#### **4.4.2. Open-Label Run-In Polyarticular Course JIA Analysis Set (OLJAS)**

The open-label run-in polyarticular course JIA analysis set (OLJAS) consists of all subjects included in the OLFAS with polyarticular course JIA.

#### **4.4.3. Open-Label Run-In ERA Analysis Set (OLERA)**

The open-label run-in ERA analysis set (OLERA) consists of all subjects included in the OLFAS with ERA.

#### **4.4.4. Open-Label Run-In PsA Analysis Set (OLPsA)**

The open-label run-in PsA analysis set (OLPsA) consists of all subjects included in the OLFAS with PsA.

## **5. GENERAL METHODOLOGY AND CONVENTIONS**

### **5.1. Hypotheses and Decision Rules**

#### **5.1.1. Hypotheses**

The primary hypothesis is that among subjects who achieve ACR30 response at Week 18, those who remain on tofacitinib will have a lower rate of disease flare up to Week 44/EoS compared to those on placebo.

From statistical perspective, the primary null hypothesis is

$$H_0 : p_t - p_c = 0 ,$$

and the primary alternative hypothesis is

$$H_0 : p_t - p_c \neq 0 ,$$

where  $p$  refers to the proportion of disease flare by Week 44/End of Study (Week 26 of the double-blind phase) for polyarticular course JIA subjects, the subscript  $c$  refers to the control group (placebo) and the subscript  $t$  refers to the treatment group.

Tofacitinib will be considered superior to placebo with respect to occurrence of disease flare by Week 44/End of Study (EoS) (Week 26 of the double-blind phase) for polyarticular course JIA subjects if the test for difference in the occurrence rate results in a p-value (two-sided) less than 0.05.

### 5.1.2. Statistical Decision Rules

In order to preserve type I error, each endpoint will be assessed sequentially using gate-keeping or step-down approach where statistical significance can be claimed for the second endpoint only if the first endpoint in the sequence meets the requirements for significance.

CCI

Analyses other than primary and key secondary analyses will not be strictly controlled for Type I error.

## 5.2. General Methods

In addition to the statistical analyses given below, all efficacy endpoints as described in [Section 3](#) will be summarized descriptively. In general, number and percent will be presented for binary variables; number, mean, median, standard deviation, quartiles, minimum, and maximum will be presented for continuous variables; estimates of median event-free time and survival probabilities by Kaplan-Meier method will be presented for time-to-event endpoints.

### 5.2.1. Analyses for Binary Data

#### 5.2.1.1. Normal Approximation Approach

Binary endpoints will be analyzed using the normal approximation approach for the binomial populations for double-blind polyarticular course JIA analysis set (DBJAS).

CCI [Redacted]

[Redacted]

[Redacted]

[Redacted]

[Redacted]

[Redacted]

### 5.2.2. Analyses for Continuous Data

For the continuous secondary endpoints, a mixed-effect model with repeated measures (MMRM) will be applied. CCI

[Redacted]

CCI [Redacted]

CCI

CCI

### 5.2.3. Analyses for Time to Event Data

The Kaplan-Meier plot will be generated for the secondary endpoint of time to flare. The log rank test will be used to compare the treatment groups.

CCI

CCI

CCI

CCI

CCI

CCI

CCI

CCI

CCI

### **6.3. Other Endpoint(s)**

#### **6.3.1. Analysis of PK Endpoints**

Please see details in the protocol and PMAP (or population PK modeling plan).

#### **6.3.2. Analysis of Exploratory Endpoints**

Exploratory or pooled analyses, if conducted utilizing the biobanked genomic and/or biomarker samples from this study, will be documented in a separate analysis plan.

### **6.4. Subset Analyses**

The primary endpoint, key secondary endpoints and some secondary endpoints (occurrence of disease flare, achieving ACR 30/50/70 and JIA ACR inactive disease at each scheduled visit in double-blind phase; time to disease flare in double-blind phase) and open-label run-in baseline demographic characteristics will be summarized by JIA category, open-label run-in baseline C-Reactive Protein (normal and above normal), geographical region (North America [US and Canada], South and Central America [Brazil, Argentina, Mexico], European Union [Poland, Belgium, Great Britain, Spain], All Other [Ukraine, Turkey, Russia, Australia and Israel]), baseline body weight (<40 kg, ≥40 kg), and age (2 to <6 years, 6 to <12 years and 12 to <18 years) by treatment and visit. Inferential statistics and forest plot for treatment comparison by the aforementioned subgroups will be performed at week 26 of the double-blind phase for the efficacy endpoints if appropriate. For time to disease flare, Kaplan-Meier analysis will be replicated for each JIA category, open-label run-in baseline CRP and age group, separately.

As said in [Section 6.2.2](#) to [6.2.4](#), for ERA subjects and PsA subjects, only descriptive statistics will be reported by treatment and visit.

### **6.5. Baseline and Other Summaries and Analyses**

None.

### **6.6. Safety Summaries and Analyses**

Safety analysis will be performed for polyarticular course JIA, ERA and PsA subjects combined together. Safety data will be reported separately for the open-label run-in phase using OLFAS and the double-blind phase using DBSAS. In addition, AE will be reported using the entire exposure period (both open-label run-in phase and double-blind phase) while the subjects are exposed to tofacitinib.

For occurrence of active uveitis (according to SUN criteria) at each scheduled visit in the open-label run-in and double-blind phase, descriptive statistics will be reported. Visit window in [Appendix 9.3](#) will be used.

All the safety data, including the following, will be summarized descriptively through appropriate data tabulations, descriptive statistics, and graphical presentations:

- Safety laboratory tests will be summarized according to Pfizer standards.
- Special attention will be given to the following safety endpoints: serious infections, cytopenias, malignancies, cardiovascular diseases, gastrointestinal perforations and validated assessments of growth and pubertal development.

### 6.6.1. Adverse Events

Adverse events will be summarized according to Pfizer data standards for each phase and for the entire study period while the subjects are exposed to tofacitinib. For the AE reported over entire study period, subjects randomized to the placebo group will only have their events and exposure during the open-label run-in phase counted, and there will be no comparisons performed.

For AE reporting for each phase, AEs will not be double counted across phases. Counting of AEs will be based on start date of AE. If the start date of an AE is in the open label phase, the end date of the AE in the double blind phase and severity of AE remained the same or became lower in both phases, then the AE will be counted in open label phase, not in the double blind phase. However, if the same AE started in the open label phase, and get worse in severity in the double blind phase, then the AE will be counted in both phases. In all these analyses attention will be restricted to assessments that occurred no more than 28 calendar days after the last dose of study drug.

AEs of special interest in double-blind phase and over the entire study period while the subjects are exposed to tofacitinib will be analyzed using incidence rates (IR), including death, serious infections, opportunistic infections excluding TB, tuberculosis, herpes zoster, malignancy excluding NMSC, NMSC (non-melanoma skin cancer), lymphoma, MACE (Major Adverse Cardiovascular Events), gastrointestinal perforations, and Interstitial Lung Disease (ILD). Adverse events of macrophage activation syndrome (MAS) will be analyzed using IR. The MAS, Deep vein thrombosis (DVT), and Pulmonary embolism (PE) will be listed.

CCI

CCI

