### **8.9. Severity Assessment**

If required on the AE CRFs, the investigator will use the adjectives MILD, MODERATE, or SEVERE to describe the maximum intensity of the AE. For purposes of consistency, these intensity grades are defined as follows:

MILD	Does not interfere with subject's usual function.
MODERATE	Interferes to some extent with subject's usual function.
SEVERE	Interferes significantly with subject's usual function.

Note the distinction between the severity and the seriousness of an AE. A severe event is not necessarily an SAE. For example, a headache may be severe (interferes significantly with the subject's usual function) but would not be classified as serious unless it met one of the criteria for SAEs, listed above.

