### **8.13. Withdrawal Due to Adverse Events (See Also the Section on [Subject Withdrawal](#))**

Withdrawal due to AEs should be distinguished from withdrawal due to other causes, according to the definition of AE noted earlier, and recorded on the appropriate AE CRF page.

When a subject withdraws because of an SAE, the SAE must be reported in accordance with the reporting requirements defined below.

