### **9.2. Efficacy Analysis**

#### **9.2.1. Analysis of Primary Endpoint**

Superiority of tofacitinib to placebo for the primary endpoint of percentage of subjects with disease flare at end of study Week 44 (Week 26 of the double-blind phase) for subjects with polyarticular course (polyarthritis RF+/RF-, extended oligoarthritis, and systemic JIA with active arthritis but without active systemic features) JIA will be tested using the normal approximation approach for the binomial populations. Subjects who discontinue from the study treatment for any reason will be considered as having a disease flare, except subjects who discontinue after maintaining JIA ACR inactive disease for at least 24 weeks in the double-blind phase. These discontinuations will be considered as non-disease flare.

Additional details of the analysis of the primary endpoint will be described in the Statistical Analysis Plan (SAP).

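### A run-in adverse event that turns serious or ends treatment after randomisation at an unchanged severity grade is left out of the double-blind adverse event count

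*SAP*

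**What the plan says.** SAP 6.6.1 summarises adverse events by phase under the sponsor's data standards and gives three counting rules.

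- Default: "Counting of AEs will be based on start date of AE".
- Run-in event ending in the double-blind phase: if "severity of AE remained the same or became lower in both phases, then the AE will be counted in open label phase", and the sentence goes on to exclude it from the double-blind phase.
- Exception: if such an event should "get worse in severity in the double blind phase, then the AE will be counted in both phases".

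Neither a change in seriousness nor discontinuation of study drug is named as a trigger.

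SAP 6.6.1 also plans incidence rates in the double-blind phase for events of special interest, including serious infections. It adds a summary over all tofacitinib exposure, in which children randomised to placebo contribute their run-in period only and no comparison is made. SAP 6.6 pools polyarticular, ERA and PsA subjects for safety and describes the summaries as descriptive.

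The protocol keeps the relevant attributes apart. Section 8.9 says: "Note the distinction between the severity and the seriousness of an AE. A severe event is not necessarily an SAE". Section 8.5.1 defines a serious infection by hospital treatment, parenteral antimicrobials or other seriousness criteria, not by grade, and requires the child to leave the study. Section 8.13 says: "Withdrawal due to AEs should be distinguished from withdrawal due to other causes".

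**The concern.** The double-blind tables are the only placebo-controlled safety comparison in this trial. Every child enters them after 18 weeks on tofacitinib, so some will carry an ongoing adverse event across randomisation. What happens to that event afterwards, on continued drug or on placebo, is part of what the comparison should show.

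The rule looks at one feature of that later course, the severity grade. Suppose a moderate infection starts in Week 17 and leads to admission in Week 20, still graded moderate. It is a serious infection after randomisation and, under Protocol 8.5.1, it ends participation. By the SAP rule it is a run-in event only.

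Efficacy and safety would then describe the same child differently. For the polyarticular cohort, Protocol 9.2.1 says: "Subjects who discontinue from the study treatment for any reason will be considered as having a disease flare", with an exception for children who stop after at least 24 weeks of inactive disease in the double-blind phase. Outside that exception, the child is a double-blind flare whose cause is not in the double-blind adverse event count.

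Serious events and withdrawals due to adverse events are likely to be few in arms of this size, so one or two misplaced cases can alter how a table reads.

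**Working it through.** The plan states no figure on this point, so there is nothing to reproduce. The check has three parts.

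**1. Apply the rule to each kind of run-in event still ongoing after the first double-blind dose.**

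| Course after first double-blind dose | Grade | Counted as written |
|---|---|---|
| Continues, not serious, no discontinuation | same or lower | open-label only |
| Worsens | higher | both phases |
| Becomes serious or leads to discontinuation | higher | both phases |
| Becomes serious or leads to discontinuation | same or lower | open-label only |
| Already severe, then becomes serious or leads to discontinuation | cannot rise | open-label only |

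The last two rows are the problem. The final row follows because Protocol 8.9 has three grades (mild, moderate, severe) and severe is the top one.

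For discontinuations, the result follows from the general rule. The visible SAP gives no separate phase rule for a table of events leading to discontinuation.

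**2. Size.**

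Inputs from the documents: about 210 children enrolled (Protocol 3), 1:1 allocation (Protocol 3), and a run-in response rate of 54% to 65% (Protocol 9.1). That rate is stated for the polyarticular cohort of about 170. Applying it to all 210 is an assumption.

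- Randomised: 210 × 0.54 = 113.4; 210 × 0.65 = 136.5.
- Per arm: 113.4 / 2 = 56.7; 136.5 / 2 = 68.25, so about 57 to 68.
- One child as a share of an arm: 1/68 = 1.5%; 1/57 = 1.8%.

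Assumptions not in the documents: 10% to 30% of children have one adverse event ongoing at randomisation, and 1% to 10% of those events later become serious or lead to discontinuation at an unchanged grade.

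Events lost per arm = arm size × share with an ongoing event × share of those that qualify.

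- Low: 57 × 0.10 × 0.01 = 0.06.
- Middle: 57 × 0.20 × 0.05 = 0.57; 68 × 0.20 × 0.05 = 0.68.
- High: 68 × 0.30 × 0.10 = 2.04.

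The range is about 0.06 to 2 per arm, or 0.1% (0.10 × 0.01) to 3% (0.30 × 0.10) of an arm.

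**3. Direction.**

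Randomisation balances the events ongoing at Week 18 in expectation. If a carried-over event is r times as likely to qualify on tofacitinib as on placebo, the tofacitinib share of lost events is r / (1 + r).

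| r | Tofacitinib share |
|---|---|
| 0.5 | 33% |
| 1 | 50% |
| 2 | 67% |
| 4 | 80% |

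No passage gives a value for r, so the documents do not determine the direction.

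**A related practical point.** Where severity is collected, Protocol 8.9 asks the investigator to "describe the maximum intensity of the AE". The worsening exception needs dated changes in grade, or a new record at each change. The visible text describes neither.

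**The case against.** **Few events are affected, and they do not vanish.** Protocol 8.9 grades severity by interference with usual function, so many events that lead to admission would also rise in grade and be counted in both phases. The remainder stay in the open-label tables and, for the tofacitinib arm, fall within the whole-exposure summary. This stands and limits the point. It does not restore the comparison: the whole-exposure summary makes none, and the open-label phase has no control.

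**Other rules may exist.** The sponsor's data standards are not reproduced, and the text after the paragraph is redacted. Either could govern the serious-event, special-interest or discontinuation tables. This stands as an uncertainty. However, the visible sentence excludes these events from the double-blind phase, so any different rule elsewhere would have to be reconciled with it.

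**Start-date attribution is defensible.** The event did begin on run-in tofacitinib. That is a good reason to keep the rule for overall counts. It is less convincing for the date a child became seriously ill or stopped treatment.

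**Laboratory withdrawals are a weak example.** Appendix 6 requires two sequential abnormal values for some withdrawals, and the first could be the Week 18 sample. Whether that makes a run-in adverse event depends on how onset is dated. Protocol 8.6 says that a repeat test alone does not create one. The point does not rest on this case.

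**The stronger reading.** A reader might infer that the lost events fall mainly on continued tofacitinib, so that the plan understates drug harm. The mechanism is plausible: half-life in JIA subjects averages about 1.8 to 2.6 hours (Protocol Table 1), so children switched to placebo are soon free of drug. But Protocol 8.3 also lists worsening of underlying disease, and signs or symptoms of drug withdrawal, as adverse events, and these could progress more on placebo. With no figure for r, the documents do not support this inference.

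**Wording.** The SAP says events are not counted twice across phases and then counts worsened ones in both. That is a general rule followed by an exception, and only a matter of drafting.

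**Conclusion.** The point holds in a limited form. The visible SAP states a rule rather than leaving a gap, and the rule removes from the double-blind count any run-in event that becomes serious or leads to discontinuation after randomisation without a higher grade. The protocol's own distinction between severity and seriousness shows that this can happen.

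The effect is probably small, with an upper end of about 2 events per arm. That rests on the assumed carry-over and progression rates, and on extending the polyarticular response rate to all 210 children. A conclusion that tofacitinib harm is understated would go beyond the documents. The case for changing the rule does not need a direction: the affected events are ones a safety reader most wants to see by arm, and one child is 1.5 to 1.8 percentage points of an arm. This is a cheap improvement, not a flaw that threatens the trial's conclusions.

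**What to change.** Amend SAP 6.6.1 as follows.

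1. Keep the start-date rule for overall adverse event counts.
2. Also count in the double-blind phase any run-in event that, after the first double-blind dose, worsens in severity, becomes serious or leads to discontinuation of study drug.
3. For the double-blind tables of serious events, events of special interest and events leading to discontinuation, use the date of that change.
4. List these run-in-onset events separately by arm.
5. Word this as a stated exception to the sentence on double counting, and say how dated changes in severity are obtained.
6. If the sponsor's standards already set a phase rule for any of these tables, cite it and reconcile it with the paragraph.

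The cost is SAP wording and minor programming, since withdrawal reasons and serious-event reports are already collected. There are two downsides. A few events will appear in both phases. Some events that began on run-in tofacitinib will be counted in the placebo arm, which can raise the placebo rate and narrow the contrast. The separate listing makes them identifiable, so a reader can see the comparison with and without them.
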